## Research Activity

Check all that apply and complete the appropriate sections as instructed.

1.  **Drug & Device:** Drugs for which an investigational new drug application is not required. Device for which (i) an investigational device exemption application is not required; or the medical device is cleared/approved for marketing and being used in accordance with its cleared/approved labeling. (Specify in the Methods section)
2.  **Blood:** Collection of blood samples by finger stick, heel stick, ear stick, or venipuncture.
3.  **Biological specimens other than blood:** Prospective collection of human biological specimens by noninvasive means that may include: urine, sweat, saliva, buccal scraping, oral/anal/vaginal swab, sputum, hair and nail clippings, etc.
4.  **Tests & Procedures:** Collection of data through noninvasive tests and procedures routinely employed in clinical practice that may include: MRI, surface EEG, echo, ultrasound, moderate exercise, muscular strength & flexibility testing, biometrics, cognition testing, eye exam, etc. (Specify in the Methods section)
5.  **Data** (medical record, images, or specimens): Research involving use of existing and/or prospectively collected data.
6.  **Digital Record:** Collection of electronic data from voice, video, digital, or image recording. (Specify in the Methods section)
7.  **Survey, Interview, Focus Group:** Research on individual or group characteristics or behavior, survey, interview, oral history, focus group, program evaluation, etc. (Specify in the Methods section)

NIH has issued a *Certificate of Confidentiality* (COC). When checked, provide the institution and investigator named on the COC and explain why one was requested. \_\_\_\_\_

Biospecimens – Categories 2 and 3
--

(2) Collection of blood samples.

- a. **From healthy, non-pregnant, adult subjects who weigh at least 110 pounds.** For a minimal risk application, the amount of blood drawn from these subjects may not exceed 550ml in an 8 week period and collection may not occur more frequently than 2 times per week.

Volume per blood draw (Baseline only): 108 ml

Volume per blood draw (Follow-up visits): 105 ml

Frequency of blood draw: Four blood draws total. Blood draw #1 can occur the day of or up to 2 weeks prior to receiving the flu vaccination. Blood draw #2 will occur the following day after vaccination. Blood draw #3 will occur 7-9 days after the vaccination. Blood draw #4 will occur 25-31 days after vaccination.

b. **From other adults and children considering age, weight, and health of subject.** For a minimal risk application, the amount of blood drawn from these subjects may not exceed the lesser of 50 ml or 3 ml per kg in an 8 week period, and collection may not occur more frequently than 2 times per week.

Volume per blood draw: \_\_\_\_\_ ml

Frequency of blood draw (e.g. single draw, time(s) per week, per year, etc.) \_\_\_\_\_

(3) Prospective collection of biological specimens other than blood: \_\_\_\_\_

#### Review of medical records, images, specimens – Category 5

**For review of existing data:** provide a date range or an end date for when the data was generated. The end date can be the date this application was submitted to the IRB.

**Date Range:**

Check all that apply (data includes medical records, images, specimens).

(5a) Only data that exists before the IRB submission date will be collected.

(5b) The study involves data that exist at the time of IRB submission **and** data that will be generated after IRB submission. Include this activity in the Methods section.

**Examples**

- The study plans to conduct a retrospective chart review and ask subjects to complete a questionnaire.
- The study plans to include subjects previously diagnosed with a specific disease and add newly diagnosed subjects in the future.

(5c) The study will use data that have been collected under another IRB protocol. Include in the Methods section and enter the IRB number from which the research material will be obtained. *When appropriate, note when subjects have provided consent for future use of their data and/or specimens as described in this protocol.*

Enter one IRB number per line, add more lines as needed

Data  Specimens  Data & Specimens \_\_\_\_\_

Data  Specimens  Data & Specimens \_\_\_\_\_

Data  Specimens  Data & Specimens \_\_\_\_\_

(5d) This study will obtain data generated from other sources. Examples may include receiving data from participating sites or an external collaborator, accessing an external database or registry, etc. Explain the source and how the data will be used in the Methods section.

(6) Video audio recording:

### HIPAA Identifiers and Protected Health Information (PHI)

Protected health information is medical data that can be linked to the subject directly or through a combination of indirect identifiers.

Recording identifiers (including a code) during the conduct of the study allows you to return to the medical record or data source to delete duplicate subjects, check a missing or questionable entry, add new data points, etc. De-identified data is medical information that has been stripped of all HIPAA identifiers so that it cannot be linked back to the subject. De-identified data is **rarely** used in the conduct of a research study involving a chart review.

**Review the list of subject identifiers below and, if applicable, check the box next to each HIPAA identifier being recorded at the time of data collection or abstraction.** Identifiers apply to any subject enrolled in the study including Mayo Clinic staff, patients and their relatives and household members.

**Internal** refers to the subject's identifier that will be recorded at Mayo Clinic by the study staff.

**External** refers to the subject's identifier that will be shared outside of Mayo Clinic.

Check all that apply:	INTERNAL	EXTERNAL
Name	X	
Mayo Clinic medical record or patient registration number, lab accession, specimen or radiologic image number	X	
Subject ID, subject code or any other person-specific unique identifying number, characteristic or code that can link the subject to their medical data	X	
Dates: All elements of dates [month, day, and year] directly related to an individual, their birth date, date of death, date of diagnosis, etc.	X	
Note: Recording a year only is not a unique identifier.		
Social Security number	X	
Medical device identifiers and serial numbers		
Biometric identifiers, including finger and voice prints, full face photographic images and any comparable images		
Web Universal Resource Locators (URLs), Internet Protocol (IP) address numbers, email address		
Street address, city, county, precinct, zip code, and their equivalent geocodes	X	
Phone or fax numbers	X	
Account, member, certificate or professional license numbers, health beneficiary numbers		
Vehicle identifiers and serial numbers, including license plate numbers		
Check 'None' when none of the identifiers listed above will be recorded, maintained, or shared during the conduct of this study. (exempt category 4)	 None	 None

### Data Analysis

#### Data Analysis Plan:

The planned analyses for Aims 1 and 2 will follow the same strategies, so for Aim 2 analyses we point out the differences needed to adapt the analyses for Aim 2.

**Aim 2.1 Test the hypotheses that vaccine type (MF59Flu vs HDFlu) or sex is associated with variations in Th cell immune outcomes:** The analysis plans for Aim 1.1 will be followed, but using the Th phenotype and cytokine production outcomes, evaluating change from Baseline to Days 8 and 28.

**Aim 2.2 Test the hypothesis that the expression of specific genes is associated with differences in Th cell immune outcomes:** Analyses will parallel those for Aim 1.2, but use differential Th cell-specific gene and miRNA expression (change from Baseline to Days 8 and 28) as independent variables to evaluate for their association with change in Th cell immune responses.

**Aim 2.3 Test the hypothesis that Th cell transcriptomic signatures mediate the association of vaccine type (or sex) with Th cell immune outcomes:** Analyses will parallel those described in Specific Aim 1.3.

**Aim 2.4 Test the hypothesis that Th cell immune outcomes and transcriptomic signatures from Aim 2.3 will predict markers of humoral immunity (HAI Ab and B cell ELISPOT response):** The analysis plans closely follow the mediation analyses described in Aim 1.4. We will test the hypothesis that Th immune response and their associated genes (Aim 2.3), predict humoral immunity (HAI Ab titer and B cell ELISPOT response) at Day 28. We will also test the hypothesis that additional genes mediate humoral immunity independently of Th responses. To achieve this, we will treat Th responses as adjusting covariates, using the regression model: By adjusting for Th response, we seek genes/genesets that are only associated with humoral immune response.

**Power:** See Specific Aim 1. We anticipate stronger signals in the transcriptomic data from purified CD4+ T cells compared to PBMCs. The increased signal to noise ratio will allow for detection of smaller effects.

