##### **Specific Aim 2: Identify CD4+ T Helper (Th) Cell Transcriptomic Signatures Associated with Sex and Immune Response to Influenza Vaccines in the Elderly.** To do this we will:

- **Aim 2.1** Test the hypotheses that vaccine type (MF59Flu vs HDFlu) and/or sex are associated with variations in Th cell immune outcomes (e.g., Th phenotype and cytokine production).
- **Aim 2.2** Test the hypothesis that the increased Ag dose in HDFlu results in greater activation/suppression of the Th cell genes/genesets previously associated with immune responses to SDFlu. We will also test the hypothesis that the MF59 adjuvant results in activation/suppression of additional specific genes/genesets in CD4+ Th cells compared to HDFlu (see Overview and Rationale of Specific Aim 2).
- **Aim 2.3** Test the hypothesis that Th cell transcriptomic signatures mediate the association of vaccine type (or sex) with Th cell immune outcomes.
- **Aim 2.4** Test the hypothesis that the Th cell immune outcomes and transcriptomic signatures from Aim 2.3 will predict markers of humoral immunity (HAI Ab and B cell ELISPOT response).

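### Aim 2.2 is stated as a vaccine effect on Th gene expression, but its documented analysis relates expression to Th response with no arm term; two products identify only a product difference

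*Protocol*

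**What the plan says.** The protocol's list under Specific Aim 2 gives Aim 2.2 two hypotheses, both with Th gene expression as the outcome. The first is that "the increased Ag dose in HDFlu results in greater activation/suppression of the Th cell genes/genesets previously associated with immune responses to SDFlu". The second is that "the MF59 adjuvant results in activation/suppression of additional specific genes/genesets in CD4+ Th cells compared to HDFlu".

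The Data Analysis Plan gives Aim 2.2 another hypothesis: "Test the hypothesis that the expression of specific genes is associated with differences in Th cell immune outcomes". Changes in Th gene and miRNA expression between Baseline and each of Days 8 and 28 are used "as independent variables to evaluate for their association with change in Th cell immune responses". No vaccine term is mentioned. The analysis is otherwise said to parallel Aim 1.2.

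The plan's opening explains its format: "for Aim 2 analyses we point out the differences needed to adapt the analyses for Aim 2". The Aim 1.2 analysis itself is not in the documents supplied.

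Under Subject Recruitment, Enrollment and Screening, 400 older adults are randomised to MF59Flu (200) or HDFlu (200). A young control group receives no vaccine. There is no SDFlu arm.

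**The concern.** A hypothesis about what vaccine does to expression needs expression as the outcome and randomised arm as the factor. The documented Aim 2.2 model has expression as the predictor and Th response as the outcome. It can be positive for a gene that tracks Th response but does not differ by vaccine, and null for a gene that vaccine shifts but that is unrelated to the measured response. Neither result answers the stated hypothesis.

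This bears on something the protocol presents as a minimum deliverable. Background section B promises to examine whether the better immunogenicity of the two vaccines comes from stronger engagement of genes already linked to SDFlu response, or from other genes.

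There is also a question of attribution. The hypotheses name antigen dose and MF59 as causes, but the trial compares two whole products. A conclusion worded as a dose or adjuvant effect would go beyond the randomised comparison.

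**Working it through.** The plan gives no alpha, power or effect size for Aim 2.2 (its power paragraph defers to Aim 1), so there is no figure to reproduce. The check compares texts, then looks at identification and at what the missing test could detect.

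**1. Aim 2 hypotheses in the two places**

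| Sub-aim | Aims list | Data Analysis Plan |
|---|---|---|
| 2.1 | Vaccine type and/or sex with Th outcomes | Same, in substance |
| 2.2 | Vaccine (dose; adjuvant) acting on Th expression | Th expression associated with Th outcomes |
| 2.3 | Th signatures mediate vaccine or sex effect on Th outcomes | Same |
| 2.4 | Th outcomes and signatures predict humoral markers | Same |

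Only 2.2 changes. The expected-results text likewise describes Aims 1.2 and 2.2 as finding genes linked to better immunogenicity.

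**2. Where else an arm test of Th expression might be**

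- SAP: arms are compared on change in HAI titre from baseline to Day 28, by Wilcoxon rank sum. Nothing on expression.
- Potential Limitations and Alternative Strategies: the kernel geneset tests relate each immune response to expression of the genes in a set, the same direction as the Aim 2.2 regression.
- Aim 2.3: tests whether "Th cell transcriptomic signatures mediate the association of vaccine type (or sex) with Th cell immune outcomes". This normally includes an arm-to-expression path, but a mediator must also relate to the outcome. Its detail defers to Aim 1.3, also not supplied.
- Aim 1.2 analysis: not supplied, so unknown.

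**3. What two arms identify**

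The Background describes MF59Flu as adjuvanted and subunit, and HDFlu as split-virus with four times the haemagglutinin (60 µg per strain against 15 µg for SDFlu). MF59Flu's antigen amount is not given, so dose is coded below as high or not, following the stated aim.

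With mean = μ + δ(high dose) + α(adjuvant) + π(subunit):

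- HDFlu mean = μ + δ
- MF59Flu mean = μ + α + π
- Difference, MF59Flu minus HDFlu = α + π − δ

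Four parameters and two arm means give a design of rank 2. The difference is estimable; δ and α separately are not. Dropping π leaves three parameters and rank 2, with the same conclusion.

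**4. What an arm test could detect**

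Subject Information says the 400 include 10% over-recruitment. Read as a 10% loss, 400 × 0.9 = 360, or 180 per arm. (Read as 400/1.1 = 364, it is 182 per arm, with almost identical results.) Assumptions: 80% power, two-sided tests, no gain from baseline adjustment.

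Detectable difference in SD units = (z(1−α/2) + 0.842) × √(2/n), with √(2/180) = 0.1054.

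- Single test, α = 0.05: (1.960 + 0.842) × 0.1054 = 0.295
- Two visits, α = 0.025 each: (2.241 + 0.842) × 0.1054 = 0.325

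The protocol plans FDR control but states no level. Assume q = 0.05, many independent tests, and a fraction π₁ truly shifted. The p-threshold is then 0.8qπ₁ / (1 − q(1 − π₁)).

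- π₁ = 0.10: 0.004/0.955 = 0.0042; (2.864 + 0.842) × 0.1054 = 0.391
- π₁ = 0.02: 0.0008/0.951 = 0.00084; (3.339 + 0.842) × 0.1054 = 0.441

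**The case against.** The strongest objection is that the supplied analysis plan lists only adaptations. If the Aim 1.2 analysis has expression as outcome and arm as factor, Aim 2.2 may inherit that. This stands. A reader might infer that the trial has no arm contrast on Th expression at all; the documents do not support that. They show only that none is designated in the text supplied, and that the Aim 2.2 hypothesis was replaced.

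Second, Aim 2.3 covers part of the gap. That also stands: a gene both shifted by vaccine and related to response is within its reach, which suits the first hypothesis, about genes already linked to SDFlu response. The second hypothesis, about additional genes, is the more exposed. Aim 2.3 is not named as the test of either.

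Third, a reader might try to prove the point with simulated detection rates. These would follow from the chosen effects. A test of a parameter set to zero rejects about 5% of the time by construction. A 0.3 SD shift gives about 81% power at unadjusted 0.05 because 0.295 SD is the 80% detectable difference. At the FDR thresholds above, the same shift has about 49% and 31% power. Such rates illustrate that the tests differ; they are not evidence about this trial.

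Fourth, a reader might infer that the protocol contradicts itself on Th sequencing. The power paragraph says "We anticipate stronger signals in the transcriptomic data from purified CD4+ T cells compared to PBMCs", and Aim 2.2 uses Day 28, while Experimental Design describes sequencing of T- and B-cell depleted PBMCs, or PBMCs, at Baseline, Day 1 and Day 8. But that section is introduced as covering transcriptional changes and innate variables at those three visits, and Day 28 blood is collected. The CD4+ assay is undescribed, which calls for clarification; no contradiction is shown.

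**Conclusion.** The concern holds in limited form. Aim 2.2 is stated as a vaccine effect on Th expression, the analysis plan substitutes an expression-to-response association, and no arm test of Th expression is designated in the documents supplied. This affects one of eight sub-aims as documented. Any statement about Aim 1.2 is inference, because its analysis is missing; confidence is therefore moderate.

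The identification point does not depend on the missing text. No model fitted to these two arms alone can separate antigen dose or MF59 from the rest of the product difference. The phrase comparing MF59 with HDFlu is testable as a product contrast, but not as an effect of the adjuvant alone.

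The primary HAI analysis is unaffected. The matter is worth correcting before the Th expression data are analysed.

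**What to change.** - Make the Aim 2.2 hypothesis the same in the aims list and the Data Analysis Plan.
- Unless the Aim 1.2 analysis already does this (in which case cite it), add a model with change in Th gene and pre-specified SDFlu-associated geneset expression as outcome and randomised arm as factor. Adjust for baseline expression, use the Aim 2.2 visits (Days 8 and 28), and apply the planned FDR control with its level stated.
- Keep the gene-outcome regression as a separately labelled step.
- Word hypotheses and conclusions as MF59Flu-versus-HDFlu product differences, not as effects of antigen dose or of MF59 alone.
- State the cell material and visits for the CD4+ sequencing.

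The cost is wording plus one more model on expression data that Aim 2.2 already needs. Arms, sample size and blood-draw visits do not change. The cost of the CD4+ assay cannot be judged, because the documents do not describe it. The downside is one more family of tests and a narrower claim.

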### Potential Limitations and Alternative Strategies for Aims 1 and 2.

False-positive associations will be controlled by our clearly defined analysis plan, the use of false-discovery rates to assess significance, and geneset/pathway analysis to maximize power and minimize false discovery. Statistical power to detect effects is driven by our sample size of 400 subjects, which is larger than most systems biology studies, including our prior study of SDFlu in older subjects where we and others were able to successfully identify transcriptomic signatures of vaccine response. Accumulation of information across multiple genes increases the percent of variability explained by the model and hence increases the likelihood of detecting effects. Our analysis approach will also test the association of each innate and Th cell immune response with the expression of all genes in a specified geneset using kernel methods. Advantages of kernel methods are the following: 1) they allow for correlations among the different genes in a geneset; 2) they are robust to when some genes are positively associated with a response, others are negatively associated with a response, and other genes in the geneset are not associated; 3) and they allow adjustment for covariates. Finally, we will evaluate data-driven genesets using WGCNA to group genes into biological modules, which is an approach we have successfully used (see Preliminary Data).

Separate mediation analyses will be performed for mRNA and miRNA. If we find both mRNA and miRNA to be separate mediators in our initial analyses, we will evaluate their joint effects as a pathway of mediators using techniques developed by VanderWeele. Other confounding factors (e.g., immunosenescence, underlying medical conditions, obesity, and CMV serostatus) will be evaluated in our analyses as potential confounders.

**Expected Results and Impact of Findings for Specific Aims 1 and 2.** Our publications and preliminary data indicate a high likelihood of identifying not only significant vaccine type-

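### Aim 2.4 would label genes as exclusively humoral from a Th-adjusted test that cannot show they are unrelated to Th

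*Protocol*

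**What the plan says.** Under Aim 2.4 the Protocol's Data Analysis Plan states a second hypothesis: "We will also test the hypothesis that additional genes mediate humoral immunity independently of Th responses". The method is regression: "we will treat Th responses as adjusting covariates". The inference drawn is "By adjusting for Th response, we seek genes/genesets that are only associated with humoral immune response".

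Three other places bear on this.

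- Aim 2.2, in the same section, uses gene and miRNA expression changes as "independent variables to evaluate for their association with change in Th cell immune responses". A gene-Th estimate will therefore exist for each gene. Nothing visible ties that estimate to the label given in Aim 2.4.
- The limitations section for Aims 1 and 2 relies on false-discovery rates. As examples of confounders to be evaluated it names "immunosenescence, underlying medical conditions, obesity, and CMV serostatus".
- The SAP's Analysis Approach plans technical replicates for all laboratory assays.

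The regression equation is missing from the text available, and so is the Aim 1.4 analysis on which Aim 2.4 is modelled ("The analysis plans closely follow the mediation analyses described in Aim 1.4"). Neither gap is counted against the plan.

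**The concern.** A non-zero gene coefficient in a model that contains Th says that the gene carries information on humoral response beyond measured Th. It is silent on whether the gene is also related to Th. A gene that drives both Th response and antibody would pass the test and be described as purely humoral.

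A second, conditional problem concerns genes that act only through Th. If Th is measured with error, adjustment removes only part of the Th route, and the remainder looks like a direct effect. If Th and humoral response share an unmeasured cause, such as pre-existing immunity, conditioning on Th induces a gene-humoral association where none exists. Either can push the flagging rate above its nominal level.

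At stake is the mechanistic conclusion. The Protocol's expected-results text wants the gene findings to guide functional studies and adjuvant design, and a dual-route or Th-mediated gene labelled as exclusively humoral would misdirect that work.

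**Working it through.** The documents give no alpha, effect size or assay reliability for Aim 2.4, so there is no planned figure to reproduce.

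**Inputs from the documents.** There are 400 older subjects, including 10% over-recruitment for drop-out and poor cell recovery (Protocol, Subject Information), so 400 × 0.9 = 360 evaluable.

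**Assumptions.** Variables have unit variance. The Th-to-HAI path is b = 0.4 and the gene-Th path is a. The direct gene effect is d. A shared cause loads u on both Th and HAI. Th reliability is R. Testing is two-sided at 5% per gene.

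**Formula.** With G gene, T measured Th and Y humoral response:

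r(GY.T) = (r_GY − r_GT·r_TY) / √[(1 − r_GT²)(1 − r_TY²)]

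where r_GY = d + ab, r_GT = a√R and r_TY = (b + u² + ad)√R. The rejection rate is Φ(c − 1.96) + Φ(−c − 1.96), with c = |atanh r|·√(n − 4).

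**1. Gene related to both Th and HAI** (a = 0.4, d = 0.2, R = 1, u = 0). Here r_GY = 0.20 + 0.16 = 0.36, r_GT = 0.40 and r_TY = 0.40 + 0.08 = 0.48. The partial correlation is (0.36 − 0.192)/√(0.84 × 0.7696) = 0.209. Then c = 0.2121 × √356 = 4.00, and the rate is Φ(2.04) = 98%. Over wider assumptions (gene-Th 0.3 to 0.5, direct effect 0.15 to 0.30, Th effect 0.3) such genes pass 76% to 100% of the time at n = 360.

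**2. Gene acting only through Th** (d = 0). The numerator becomes ab − aR(b + u²).

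- R = 1, u = 0: the numerator is 0, so the rate is exactly 5%.
- Error only, a = 0.5, R = 0.7: 0.20 − 0.14 = 0.06. r = 0.06/√(0.825 × 0.888) = 0.070, c = 1.32, rate 26.3%.
- Shared cause only, a = 0.5, u = 0.5: 0.20 − 0.325 = −0.125. r = −0.125/√(0.75 × 0.5775) = −0.190, c = 3.63, rate 95.2%.
- Both, a = 0.5, u = 0.5, R = 0.7: 0.20 − 0.2275 = −0.0275. r = −0.036, c = 0.68, rate 10.5%.

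**3. Adding a baseline proxy P for the shared cause** (proxy reliability 0.8). Use r_GP = 0, r_TP = u√(0.8R) and r_YP = (u + bu)√0.8, take each correlation partial on P, apply the formula again, and use √(n − 5). For a = 0.5, u = 0.3, R = 0.7: r_GY.P = 0.216, r_GT.P = 0.429 and r_TY.P = 0.361. The partial correlation is 0.072 and the rate is 27.7%.

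Rates for genes acting only through Th, n = 360:

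| a | u | R = 1 | R = 0.7 | R = 1, proxy | R = 0.7, proxy |
|---|---|---|---|---|---|
| 0.3 | 0 | 5.0% | 11.6% | 5.0% | 11.5% |
| 0.5 | 0 | 5.0% | 26.3% | 5.0% | 26.3% |
| 0.3 | 0.3 | 9.4% | 6.5% | 5.2% | 11.9% |
| 0.3 | 0.5 | 50.0% | 6.7% | 8.8% | 13.1% |
| 0.5 | 0.3 | 20.3% | 10.0% | 5.8% | 27.7% |
| 0.5 | 0.5 | 95.2% | 10.5% | 18.9% | 31.7% |

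Simulations of these set-ups agree: 11-28% with error only, 9-96% with a shared cause only, 6-11% with both, and 11-33% with both plus the proxy.

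The offset in the R = 0.7 column arises because error pushes the coefficient up while a shared cause that raises both Th and HAI pushes it down. A shared cause with opposite effects on the two would not offset.

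**4. Under false-discovery control.** This was simulated with Benjamini-Hochberg at an assumed 5%, n = 400, 500 Th-only genes, 9,500 null and 100 with a true direct effect, and no shared cause. With gene-Th and Th-humoral correlations both 0.5, the realised false-discovery proportion is 4.6% at R = 1, 6.2% at 0.9, 11.4% at 0.8 and 22.7% at 0.7. With both correlations 0.3 it stays at 4.6-6.0% for R from 0.9 to 0.7.

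**The case against.** The best defence is that the stated hypothesis concerns genes acting independently of Th, and that detecting a real direct effect is power for that hypothesis. On that reading the 98% is not an error rate. The sentence also says only that such genes are sought, the word additional sets them apart from the Aim 2.3 genes, and Aim 2.2 tests gene-Th association directly. This stands as far as it goes: 98% is a mislabelling rate for the exclusive claim and is not a false-positive rate for a direct effect. It does not rescue the exclusive claim. No visible rule connects Aim 2.2 to the label, and a non-significant Aim 2.2 result would not show that a Th association is absent.

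A reader might go further and infer that the adjusted test necessarily produces false Th-independent genes. The documents do not support that. With Th measured exactly and no shared cause, the rate is nominal. The largest figures need strong confounding together with perfectly measured Th, and scaling the paths to unit residual variances lowers the shared-cause range to 8-37%. Under false-discovery control with moderate correlations the excess is negligible.

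A reader might also infer that the plan omits baseline HAI or any confounding sensitivity analysis. That cannot be established. The confounder list is given as examples, and the covariates may sit in the Aim 1.4 text or the equation, neither of which is available.

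**Conclusion.** The inference to exclusivity does not follow from the test. This needs no assumption and cannot depend on the missing equation, because the text itself says that Th enters as an adjusting covariate. The 98% illustrates the consequence for one assumed gene.

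Excess flagging of genes that act only through Th is possible but conditional. It requires Th assay error, unmeasured common causes, or both, and the documents give a size for neither. Across the assumed settings the per-gene rate runs from 5% to 95%, and is about 7-10% when both problems are present in the form assumed. It should be stated as a risk to be examined.

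It would be tempting to conclude that adjusting for baseline HAI settles the matter. It does not: with Th reliability 0.7, adding the proxy alone raised the rate from about 7-10% to about 12-32%, because it removes the bias that was offsetting the measurement error.

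This concerns one clause of a mechanistic aim. The SAP's primary Wilcoxon comparison of HAI change is not affected.

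**What to change.** 1. Reword the Aim 2.4 inference to: *associated with humoral response beyond the measured Th response*.
2. Report, beside each flagged gene, its Th association and confidence interval from Aim 2.2. Use *only humoral* or *Th-independent* solely where that interval excludes a prespecified material association.
3. Add a sensitivity analysis that covers both Th measurement error, using the replicates planned in the SAP, and unmeasured Th-humoral confounding. The reference list already contains a paper on sensitivity analysis for causal mediation (entry 108). Technical replicates inform assay error only, so a range of lower reliabilities should be shown too.
4. Baseline HAI may be added as a covariate, but only together with the measurement-error analysis.

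The cost is wording and analysis time; no new visits or samples are needed. Fewer genes will be called Th-independent, and the bound must be chosen with care. At n = 360 the standard error of a standardised coefficient is about 1/√360 = 0.053. With a 90% interval and a bound of 0.10, a gene with truly no Th association qualifies only if its estimate lies within 0.10 − 1.645 × 0.053 = 0.013 of zero, which happens about 20% of the time. With a bound of 0.15 the figure is about 77%. Both are for one Th outcome, before multiplicity.
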